5.3 Lifestyle restrictions

There are no life style restrictions, with the exception of contraceptive use and taking alcohol and investigational product at the same time.

5.3.1 Pregnancy

The following restrictions apply while the patient is receiving study treatment and for the specified times before and after.

- 1 Female patient of childbearing potential
- Female patients of childbearing potential who are not abstinent and intend to be sexually active with a non-sterilized male partner must use an acceptable method of contraception (Table 5) from the time of Screening throughout the total duration of the drug treatment and the drug washout period (4 weeks) after the last dose of study treatment. Cessation of birth control after this point should be discussed with a responsible physician. Periodic abstinence, the rhythm method, and the withdrawal method are not acceptable methods of contraception. Female patients should refrain from breastfeeding throughout this period.
- 2 Male patients are not required to use contraception

Please note, females of childbearing potential are defined as those who are not surgically sterile (ie, bilateral salpingectomy, bilateral oophorectomy, or complete hysterectomy) or post-menopausal.

Women will be considered post-menopausal if they have been amenorrhoeic for 12 months without an alternative medical cause. The following age-specific requirements apply:

- Women <50 years of age would be considered post-menopausal if they have been amenorrhoeic for 12 months or more following cessation of exogenous hormonal treatments and if they have luteinizing hormone and follicle-stimulating hormone levels in the post-menopausal range for the institution.
- Women ≥50 years of age would be considered post-menopausal if they have been amenorrhoeic for 12 months or more following cessation of all exogenous hormonal treatments, had radiation-induced menopause with last menses >1 year ago, or had chemotherapy-induced menopause with last menses >1 year ago.
- Women who are surgically sterile (ie, bilateral salpingectomy, bilateral oophorectomy, or complete hysterectomy) are eligible.

Barrier/intrauterine methods	Hormonal methods
 Copper T intrauterine device Levonorgestrel-releasing intrauterine system (eg, Mirena®)^a 	 Implants: Etonogestrel-releasing implants (eg, Implanon® or Norplant®) Intravaginal Devices: Ethinylestradiol/etonogestrel-releasing intravaginal devices (eg, NuvaRing®) Injection: Medroxyprogesterone injection (eg, Depo-Provera®) Combined Pill: Normal and low dose combined oral contraceptive pill Patch: Norelgestromin/ethinylestradiol- releasing transdermal system (eg, Ortho Evra®) Minipill: Progesterone based oral contraceptive pill using desogestrel: Cerazette® is currently the only highly efficacious progesterone based pill

Acceptable methods of contraception (<1% failure rate) Table 5

This is also considered a hormonal treatment

5.3.2 Alcohol intake

Investigational product should not be taken within an hour of ingesting alcohol. There are no restrictions on combining IP intake with caffeine or nicotine intake, but it is recommended to take the IP with food.

5.3.3 **MRI** procedures:

Patients will be instructed to drink at least 250 mL water within 1 hour before the scan.

5.4 **Pre-screen and screen failures**

The study will include a two-step screening procedure:

- Pre-screening (Visit 1): Patients with sUA <6.0 mg/dL, eGFR <25 mL/min/1.73 m² or • UACR <30 mg/g will be classified as pre-screen failures. A single repeat test is permitted if initial sUA, eGFR or UACR results are not in the eligible range.
 - Patients are eligible to pre-screen up to 2 times. There are no time restrictions between the two pre-screening visits.
 - The visit at which the pre-screening criteria are met should be within Weeks -6 to -1.
 - Once patients have met the criteria set in pre-screening, patients are eligible for _ screening.
 - If a patient passes pre-screening but does not yet satisfy the inclusion/exclusion criteria, the subject may wait to screen at the discretion of the investigator.
- Screening (Visit 2): Patients who do not meet all eligibility criteria based on the full Visit 2 assessment will be classified as Screen Failures.

- A single repeat of an out-of-eligibility range assessment is permitted.
- Patients can undergo screening up to 2 times.
- The same IXRS ecode should be used for the re(pre)screened patient.

Screen failures are defined as patients who signed the ICF to participate in the clinical study but are not subsequently randomly assigned to study treatment. A minimal set of screen failure information is required to ensure transparent reporting of screen failure patients to meet the Consolidated Standards of Reporting Trials (CONSORT) publishing requirements and to respond to queries from regulatory authorities. Minimal information includes demography, screen failure details, eligibility criteria, and any SAE.

These patients should have the reason for study withdrawal recorded in the electronic case report form (eCRF).

6 STUDY TREATMENTS

Study treatment is defined as any IP (including marketed product comparator and placebo) or medical device(s) intended to be administered to a study participant according to the study protocol. Study treatment in this study refers to verinurad, allopurinol or placebo.

Study treatment is to be administered in the morning and will be generally better tolerated if taken in association with food. Patients should be advised to maintain adequate hydration.

6.1 Treatments administered

6.1.1 Investigational products

	IP 1	IP 2
Study treatment name:	Verinurad or matching placebo	Allopurinol or matching placebo
Dosage formulation:	Capsule	Tablet
Route of administration	Oral	Oral
Dosing instructions:	3, 7.5, or 12 mg to be taken, one time a day	100, 200, or 300 mg to be taken, one time a day
Packaging and labelling	Verinurad capsules will be packaged in bottles. Each bottle will be labelled in accordance with Good Manufacturing Practice (GMP) Annex 13 and per country regulatory requirement	Allopurinol tablets will be packaged in bottles. Each bottle will be labelled in accordance with Good Manufacturing Practice (GMP) Annex 13 and per country regulatory requirement
Provider	AstraZeneca	AstraZeneca

Table 6Study treatments (prior to Protocol Version 5.0)

IP Investigational product

At the time of implementation of Protocol Version 5.0, a new dosing regimen will be introduced to assess the higher dose of 24 mg verinurad. Patients in the 3 mg verinurad cohort who will have Visit 9 after the amendment implementation in the prospective country/site and who have signed ICF for the new dosing regimen will be switched to 24 mg dose at Visit 9. Patients who do not consent should be discontinued from the study at a subsequent visit. To introduce the new 24 mg dose, a new dosing regimen across treatment arms will be initiated to maintain blinding in all study cohorts. All patients in the new dosing regimen will receive 2 capsules, as patients switched from 3 mg to 24 mg dose will receive two 12-mg verinurad capsules, and the bottles differentiated by colour, will be administered to all other patients. Patients on 24 mg verinurad need to take two 12-mg verinurad capsules. To match, patients in the other arms must take 2 capsules for blinding purposes. Patients will be instructed to take one capsule out of two different bottles every day. Allopurinol dosing will remain the same.

	IP 1	IP 2
Study treatment name:	Verinurad or matching placebo	Allopurinol or matching placebo
Dosage formulation:	Capsule	Tablet
Route of administration	Oral	Oral
Dosing instructions:	3*, 7.5, or 12 mg to be taken, one time a day from two differently coloured bottles Patients from 3 mg dose who will be switched to 24 mg will receive 24 mg as two 12-mg capsules**	100, 200, or 300 mg to be taken, one time a day
Packaging and labelling	Verinurad capsules will be packaged in bottles. Each bottle will be labelled in accordance with Good Manufacturing Practice (GMP) Annex 13 and per country regulatory requirement	Allopurinol tablets will be packaged in bottles. Each bottle will be labelled in accordance with Good Manufacturing Practice (GMP) Annex 13 and per country regulatory requirement
Provider	AstraZeneca	AstraZeneca

Table 7Study treatments (after implementation of Protocol Version 5.0)

IP Investigational product

*3 mg verinurad capsules will only be used for down-titration for patients on the new dosing regimen as of Protocol Version 5.0.

**Patients on 24 mg verinurad need to take two 12-mg verinurad capsules. To match, patients in the other treatment arms must take 2 capsules to maintain the blind. Patients will be given two different bottles with differently coloured labels. Patients will be instructed to take one capsule from each of two different bottles every day. Patients who do not tolerate the new dosing regimen will be down-titrated to the initial dosing regimen (ie, patients on 24 mg will be down-titrated to 3 mg, and patients in other cohorts will not be dispensed the matching placebo capsule).

The verinural capsules release verinural over 8 h, hence the formulation is referred to as ER8 (Extended Release over 8 h).

Study treatments will be titrated in discrete steps as shown in Table 8. Titration steps will be spaced at 4-week (± 1 week) intervals to minimise the risk of skin reactions to allopurinol. Patients unable to tolerate the stepped dosage may be down-titrated only by reversing the assigned steps within treatment group, and verinurad and allopurinol dosages cannot be unpaired from the titration schedule. Patients who cannot tolerate the step-1 dose will be discontinued from IP and be followed for the remainder of the study.

At Visit 5 (approximately 8 weeks after randomisation) through Visit 9, titration to step-3 target dose will only be allowed if the patient's eGFR was \geq 30 mL/min/1.73m² at Visits 3 and 4.

When the new dosing regimen is introduced under Protocol Version 5.0, patients who were down-titrated due to intolerance in the initial dosing regimen will not switch treatment to the new dosing regimen. These patients will instead remain on the same treatment after Visit 9.

Patients who do not tolerate the new dosing regimen will be down-titrated to the initial dosing regimen (ie, patients on 24 mg will be down-titrated to 3 mg, and patients in other cohorts will not be dispensed the matching placebo capsule).

Patients will only be allowed to switch to the new dosing regimen introduced under Protocol Version 5.0 if the patient's eGFR was \geq 30 mL/min/1.73m² at Visit 8. Management of patients with eGFR <30 mL/min/1.73m² at Visit 9 should be discussed with the medical monitor.

In case patient down-titration was done in error, the patient can be up-titrated only after consultation with the medical monitor.

	Step 1 - titration	Step 2 - titration	Step 3 - target dose
	(verinurad/allopurinol)	(verinurad/allopurinol)	(verinurad/allopurinol)
High Dose (mg)	3/100	7.5/200	12/300
Intermediate Dose (mg)	3/100	7.5/200	7.5/300
Low Dose (mg)	3/100	3/200	3/300
Allopurinol alone (mg)	0/100	0/200	0/300
Placebo (mg)	0/0	0/0	0/0

Table 8Titration schedule

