4.1.2.6 Week 12 (Visit 6)

- Place phone calls on the day before the visit to remind patients to not take drug at home before this visit and to record the time and date of the last dose taken
- Visit to be scheduled in the morning to permit PK blood collection
- Collect first morning void samples from 3 days before visit (for primary CCI biomarkers)
- Collect untaken study medication
- Update concomitant medication
- Record AEs
- Perform brief PE
- Record vital signs
- Record weight
- Obtain ECG
- Obtain blood samples for clinical chemistry and haematology, efficacy assessments (s-UA, creatinine, eGFR, Cystatin C, NT-proBNP)
- Obtain pre-dose PK blood samples (PK should be collected together with sUA) in all patients
- Patients take drug at clinic (time of drug intake should be recorded)
- Obtain post-dose PK and sUA blood samples in each of the four following time windows:
 (1) 3 to 4, (2) 4 to 5, (3) 5 to 6 and (4) 8 to 9 h in patients participating in the PK substudy
- Collect untaken study medication
- Obtain urine samples for safety assessment (dipstick urinalysis
- Perform pregnancy urine dipstick test for women of childbearing potential; after 2 positive urine tests, a serum pregnancy test is to be done by central laboratory
- IVRS/IWRS transaction and dispense titration Step-3 dose (Note: Titration to step-3 target dose will only be allowed if the patient's eGFR was ≥30 mL/min/1.73m² at Visits 3 and 4.)
- Dispense containers for morning voids

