7.1.1 Temporary interruption of study treatment

Patients may temporarily interrupt IP administration, for instance based on criteria for Appendix F. Temporary interruption of IP does not mean discontinuation of follow-up or termination of study participation. Study assessments should continue. When the IP is resumed, last dose taken should be administered again. If temporary interruption of IP occurred during titration step, the patient should resume titration with the last tolerable dose given. In the event of an interruption exceeding 1 month the administration of IP can be re-titrated to avoid allopurinol induced hypersensitivity reactions, after communication with the sponsor or sponsor's representative.

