8.10 Guidelines, study assessments, and procedures during COVID-19 pandemic

In view of the ongoing and emerging novel coronavirus (COVID-19) pandemic spreading worldwide, the safety and well-being of our study participants is of primary importance. To protect the safety and well-being of study participants, this section will provide guidelines on study assessments and procedures during this period.

- 1 Every effort should be made to follow the clinical study protocol (CSP). Participant safety is paramount, and the investigator should continue to reassess the risk/benefit of continued study involvement for each study participant.
- 2 Investigational study sites must comply with local public health rules.
- 3 If a study participant is diagnosed with COVID-19 or is suspected to have COVID-19, they should follow the local area treatment and quarantine guidance.
 - (a) Please accurately document all diagnoses, procedures, assessments, dosing interruptions, and sequelae in the eCRFs. All AEs/SAEs should be reported in line with instructions for safety reporting documented in the CSP.
 - (b) If a COVID-19 AE/SAE is reported, the investigator should determine whether the participant's investigational product should continue, be interrupted, or stopped in accordance with the CSP.
 - (c) Patients with confirmed or suspected COVID-19 infection with moderate to severe symptoms may be at risk of dehydration or hypoxia. In case of such events the PI should consider IP interruption until symptoms improve.
- 4 If a study participant is unable to attend clinic visits, and/or receive study intervention, the site staff should keep in close contact with the study participant(s), preferably through telephone calls, to maintain awareness of their status.
- 5 If a patient cannot be seen on site, please consider the following options:
 - (a) Conducting the visits in the patient's home by study personnel or other trained professionals. In addition, third party vendor personnel may be utilised to conduct assessments.

- (b) Conducting the visit by phone, with urine samples, investigational product and urine sample collection containers shipped or otherwise transported between site and patient. The collection and analysis of safety blood samples at an alternative healthcare facility should be considered. Local lab results will not be collected or stored in the study database but will help the investigator to assess patient safety.

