F 2.1 Patients with baseline eGFR \geq 40 mL/min/1.73 m²

F 2.1.1 Serum creatinine increase to \geq 1.5-fold from baseline

- Assess the patient to identify and manage any potential contributing factor. Correct any dehydration and ensure the patient is well hydrated prior to next renal safety monitoring visit.
- At the investigator's discretion, the patient may continue with study treatment, and retest of serum creatinine should be performed the following week. If the underlying cause (eg, dehydration) is still present at the next evaluation, the investigator should carefully consider if the retesting should be postponed for another week.
- Patient should attend the following week for repeat serum creatinine measurement. If an underlying potentially treatable cause (eg, dehydration) is still present, the investigator should treat this appropriately and postpone testing for up to a week.
- Subsequent management will depend on the repeat measurement(s):
 - If serum creatinine <1.5-fold of baseline value for two successive measurements, the patient may restart/continue with study treatment and the original study visit schedule.
 - If repeat serum creatinine is between ≥1.5 to <2.0-fold of baseline value, the patient should be evaluated every 1 to 2 weeks. During this evaluation period, the randomised treatment can be temporarily interrupted at the investigator's discretion. If serum creatinine is <1.5-fold of baseline value during the evaluation period, study treatment may be restarted/continued on the original study visit schedule.
 - If serum creatinine ≥2.0-fold of baseline value for 2 successive measurements (including the original high value if applicable), randomised treatment should be permanently discontinued and the patient should be followed up as per study schedule.

F 2.2 Patients with baseline eGFR <40 mL/min/1.73 m²

The CKD-EPI formula (Michels et al 2010) should be used to estimate GFR for enrolment criteria, baseline value and subsequent on-study measurements.

More intense renal monitoring and discontinuation are based on % drop from the baseline value.

F 2.2.1 If eGFR drops to <75% of the baseline value

- Assess the patient to identify and manage any potential contributing factor. Correct any dehydration and ensure the patient is well hydrated prior any future evaluation.

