- At the investigator's discretion, the patient may continue with study treatment and retest of serum creatinine should be performed within 7 days. If the underlying cause (eg, dehydration) is still present at the next evaluation, the investigator should carefully consider if the retesting should be postponed for another week.
- Subsequent management will depend on the repeat measurement(s):
 - If eGFR is >75% of the baseline value on 2 successive measurements, the patient may restart/ continue with study treatment on the original study visit schedule.
 - If the repeat eGFR value is between 60% and 75% of the baseline value, the patient should be evaluated every 1 to 2 weeks for serum creatinine measurements/ GFR estimation. During this evaluation period, the randomised treatment can be temporarily interrupted at the investigator's discretion. If eGFR returns to >75% of baseline value during the evaluation period, study treatment may be restarted/ continued on the original study visit schedule.
 - If eGFR is <60% of the baseline value on 2 successive measurements, randomised treatment should be permanently discontinued, and the patient should be followed up as per study schedule.

Examples of eGFR changes and triggered actions

Baseline eGFR (mL/min/1.73 m ²)	Intense renal monitoring ± temporary interruption of treatment eGFR (mL/min/1.73 m ²)	Permanently discontinue randomised treatment eGFR (mL/min/1.73 m ²)
39	23 to 29	<23
36	21 to 27	<21
32	19 to 24	<19
28	17 to 21	<17
25	15 to 19	<15

REFERENCE

Michels et al 2010

Michels WM1, Grootendorst DC, Verduijn M, Elliott EG, Dekker FW, Krediet RT. Performance of the Cockcroft-Gault, MDRD, and new CKD-EPI formulas in relation to GFR, age, and body size. Clin J Am Soc Nephrol. 2010 Jun;5(6):1003-9.

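### If an interruption delays titration step 3 past Visit 5, the eGFR condition still reads only Visits 3 and 4, so a dose increase is permitted at a known current eGFR below 30

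*Supplement*

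**What the plan says.** **The condition.** Section 6.1.1 states: "At Visit 5 (approximately 8 weeks after randomisation) through Visit 9, titration to step-3 target dose will only be allowed if the" patient's eGFR was at least 30 mL/min/1.73 m² at Visits 3 and 4. The visit-by-visit procedures repeat it. At Week 12 (Section 4.1.2.6), for example: "Titration to step-3 target dose will only be allowed if the patient's eGFR was" at least 30 at those same two visits. Table 1 footnote j and Sections 4.1.2.5 to 4.1.2.8 carry the same condition for Visits 5 to 8. The version history for Version 4 describes it as limiting up-titration where eGFR is low.

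**How step 3 can be late.** Section 7.1.1 provides: "If temporary interruption of IP occurred during titration step, the patient should resume titration with the last tolerable dose given". Only for an interruption longer than 1 month does it mention re-titration "after communication with the sponsor or sponsor's representative". Section 8.10, item 3(c), covers moderate to severe COVID-19: "In case of such events the PI should consider IP interruption until symptoms improve". It sets no eGFR condition for restarting.

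**The renal safety rules.** For baseline eGFR below 40, Appendix F 2.2 says: "More intense renal monitoring and discontinuation are based on % drop from the baseline value". Under F 2.2.1, "If eGFR is >75% of the baseline value on 2 successive measurements, the patient may restart/ continue with study treatment", and "If eGFR returns to >75% of baseline value during the evaluation period, study treatment may be restarted/ continued on the original study visit schedule".

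**The comparison within the plan.** The Version 5.0 switch at Visit 9 requires eGFR of at least 30 at Visit 8, the visit just before. Patients below 30 at Visit 9 are to be discussed with the medical monitor (Sections 4.1.2.9 and 6.1.1).

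**The concern.** When step 3 is given on time, Visit 4 is usually the newest result available, so the condition works as intended. When step 3 comes later, newer eGFR values exist but the condition does not read them. A patient can meet the written requirement on values from Weeks 0 and 4 while the investigator holds a current value under the protocol's own limit of 30.

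What is at stake is individual safety in a small group. Section 6.5 notes a raised allopurinol hypersensitivity risk with ACE inhibitors or diuretics, especially in renal impairment, and an ACE inhibitor or ARB is expected background therapy. Section 4.3 says low renal function raises verinurad exposure. Step 3 increases allopurinol in all four active arms and verinurad in the High arm.

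**Working it through.** The plan gives no figure to reproduce here. The check compares the rules and the timing.

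**1. Inputs.** Visit weeks come from Table 1: Visit 3 at Week 0, then Visit 4 at 4, Visit 5 at 8, Visit 6 at 12, Visit 7 at 20 and Visit 8 at 34, each of these ±1 week. Steps are 4 ±1 weeks apart (Section 6.1.1) and doses are in Table 8. eGFR is measured at each of these visits. Section 6.3 masks sUA and UACR reports but does not list eGFR, so the investigator sees it.

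**2. When a delayed step 3 falls.** An interruption of up to 1 month that starts by Week 8 ends by 8 + 4.3, or about Week 12. I assume steps are taken at scheduled visits.
- Resumed at step 2 before Visit 6, step 3 falls at Visit 6.
- Resumed at step 2 after Visit 6, or at step 1 before it, step 3 falls at Visit 7.
- Resumed at step 1 after Visit 6, step 3 falls at Visit 8.

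**3. Age of the values at that point.**
- Visit 6: the Visit 4 value is 12 − 4 = 8 weeks old (11 − 5 = 6 to 13 − 3 = 10). The preceding visit's value is 12 − 8 = 4 weeks old.
- Visit 7: 20 − 4 = 16 weeks (19 − 5 = 14 to 21 − 3 = 18). Preceding visit: 20 − 12 = 8 weeks.
- Visit 8: 34 − 4 = 30 weeks (33 − 5 = 28 to 35 − 3 = 32). Preceding visit: 34 − 20 = 14 weeks.

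**4. Whether Appendix F 2.2.1 closes the gap.** Its limit is 0.75 × baseline eGFR:
- baseline 30: 22.5
- baseline 36: 27.0
- baseline 39: 29.25

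It reaches 30 only at 30 / 0.75 = 40, where F 2.2 stops applying. So for every baseline from 30 to 39, a value can lie above the restart limit and below 30.

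**5. Route through Appendix F (constructed example).** Monitoring baseline and Visit 3 eGFR are 36, and Visit 4 is 34. In Week 6 the repeat value is 26, and 26/36 = 72.2%, so drug may be interrupted. Two later values of 28 give 28/36 = 77.8%, above 75%, and drug is restarted at step 2 in Week 9. The interruption lasted 3 weeks, so Section 7.1.1 requires no sponsor contact. Visit 6 comes 3 weeks after restart, inside the 4 ±1 week spacing. The condition is met on 36 and 34, although the latest value is 28.

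**6. Route through Section 8.10.** The same patient stops in Weeks 6 to 9 for COVID-19, and Visit 5 shows 28. At 77.8% the F 2.2.1 threshold is not crossed. The restart carries no eGFR condition, and Visit 6 is again decided on 36 and 34.

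**7. Size of the step.** Allopurinol 300/200 = 1.50 (+50%). Verinurad in the High arm 12/7.5 = 1.60 (+60%).

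For baseline eGFR of 40 or more, Appendix F 2.1 works in multiples of creatinine. The documents do not give the constants needed to convert these to eGFR, so the point is not extended to those patients.

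**The case against.** **The condition is necessary, not sufficient.** It restricts step 3 and does not order it, so the investigator may hold the dose. This stands, and it is why the point is minor. It does not alter the fact that nothing written requires the hold.

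**A falling eGFR does not go unexamined.** A reader might infer that Appendix F is silent in the COVID-19 route. The documents do not support that. The note to Table 14 in Section 8.2.1 refers any out-of-range creatinine to Appendix F, whose Section F 2 asks the investigator to look for the cause and manage it. Section 8.10, item 1, also asks for continuing risk/benefit reassessment. Only the F 2.2.1 percentage threshold is not met. These duties call for assessment but set no bar to the increase.

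**The later notes may simply be refill notes.** Table 1 lists step-3 dispensing at every visit from Visit 5, so the early decision may be meant to carry forward. A patient titrated on time whose eGFR later falls to 28 stays on step 3, and no document shows that step 3 at 28 is unsafe. That is fair. The point therefore concerns only a first increase from step 2, which is what the condition was added to restrict.

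**The scope is narrow.** Interruptions over 1 month involve the sponsor or the medical monitor. The Appendix F route also assumes that step 2 still counts as the last tolerable dose. On the plan's estimated dates, completion in Q4 2021 less 60 + 4 weeks puts the last randomisation at about 9 October 2020 and the last Visit 5 at about 4 December 2020, soon after this version's date of 18 November 2020. That inference further limits the number of patients this version would govern.

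**Conclusion.** The gap is real but small. After an interruption of up to 1 month during titration, step 3 at Visit 6, 7 or 8 is decided on Visits 3 and 4 alone. The protocol then permits the increase at a known eGFR below its own limit, with no required consultation. For baseline eGFR 30 to 39 the Appendix F limits do not prevent this.

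The conclusion rests on titration resuming at scheduled visits and on the literal wording of the condition. The documents do not give the number affected; it is likely to be few. The change is optional.

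Three broader readings are not supported:
- That the gap runs through every later visit. Visit 9 already refers eGFR below 30 to the medical monitor, and Visits 11 to 14 apply only to patients who passed Week 60 before Version 5.0.
- That patients already on step 3 need an eGFR floor of 30. The plan sets none, and nothing here shows that one is needed.
- That power or the primary analysis is affected. No such effect is shown.

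**What to change.** In Section 6.1.1, Table 1 footnote j and Sections 4.1.2.5 to 4.1.2.8, replace the note with wording to this effect:

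*A first increase from step 2 to step 3 requires eGFR ≥30 mL/min/1.73 m² at Visits 3 and 4 and in the most recent result available to the investigator before dispensing (central, or local if visits are held off site). Otherwise hold at step 2 and discuss with the medical monitor. Patients who continue or resume step 3 are managed under Appendix F.*

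Local results are included because Section 8.10 allows safety bloods at another facility, and those results are not stored in the study database. Table 2 footnote i and Section 4.1.2.9 need no change.

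The plan's limit of 30 is kept and no new sample is needed. An on-time step 3 at Visit 5 is usually unaffected, because Visit 4 is then the latest available result. At Visit 7 or 8 the latest scheduled value may itself be 8 or 14 weeks old, but it is newer than Visit 4.

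The cost is the protocol wording, one check at dispensing and a few more patients held at step 2. The IVRS/IWRS manual is not shown, so a check in the dispensing system may also be needed.
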